- ✓ If Hb is >13.0 g/dL and ≤ 13.5 g/dL, and there has been a sudden increase in Hb (more than 2.0 g/dL change in past 4 weeks*), discontinue darbepoetin alfa injection and resume at 1 step reduced dosage after Hb falls to ≤ 13.0 g/dL.
- ✓ If Hb is >13.5 g/dL, discontinue darbepoetin alfa injection and resume at 1 step reduced dosage after Hb falls to ≤ 13.0 g/dL.
- ✓ If Hb is maintained in the range of 11.0–12.5 g/dL, existing dosage may be doubled and dose interval extended from once every 1 week to once every 2 weeks, or from once every 2 weeks to once every 4 weeks.
- ✓ If Hb levels do not reach target levels even with dosage of 180 µg, halve existing dosage and reduce dose interval from once every 4 weeks to once every 2 weeks, or from once every 2 weeks to once every 1 week.

*Calculate Hb change rate using the Hb measurement closest to 4 weeks prior to the day of dosage adjustment (in the range of 3 to 5 weeks). A rate of change greater than 0.5 g/dL/week constitutes “sudden increase.” If Hb was not measured 3 to 5 weeks prior to the day of dosage adjustment, use the measurement made immediately prior to 5 weeks before the day of dosage adjustment.

(3) Administration method

Subcutaneous administration (initial dose after completion of scheduled tests on the first day of the treatment period)

Rationale

(1) MT-6548 Tablet

The dosage adjustment algorithm was set in order to avoid excessive Hb increase with reference to target Hb values in nephrogenic anaemia therapy according to JSDT's "Guideline for Renal Anemia in Chronic Kidney Disease 2015."

(2) Darbepoetin alfa injection

Dosage for darbepoetin alfa (recombinant) (product name: Nesp® Injection) was set according to the drug's package insert.

The dosage adjustment algorithm was set in order to avoid excessive Hb increase with reference to target Hb values in nephrogenic anaemia therapy according to JSDT's "Guideline for Renal Anemia in Chronic Kidney Disease 2015."

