*⁵: “Period from the day of administration of darbepoetin alfa to the day of next administration of darbepoetin alfa”. However, the first treatment period (days) during the scheduled study visit period should be “period from the start date during the scheduled study visit period to the day before the day of the first darbepoetin alfa administration date after the start date during the scheduled study visit period” and the last treatment period (days) should be “from the last day of darbepoetin alfa administration during the scheduled study visit period to the day before the day of the last treatment or the day before discontinuation during the scheduled study visit period”.

The following formula should be used when no darbepoetin alfa is administered during the scheduled study visit period.

Mean weekly dose of darbepoetin alfa = Weekly dose of darbepoetin alfa immediately before the scheduled study visit period.

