4.9 Mean daily dose/mean weekly dose

Mean daily dose of MT-6548 during each scheduled study visit period* = (Daily dose based on the physician's prescription \times Period of administration (days)^{*3} of the corresponding dose^{*2} between the scheduled study visits*/Period between the schedule study visits (days)^{*4}

Mean weekly dose of darbepoetin alfa during each scheduled study visit period* = Daily dose based on the physician's prescription \times Period of administration (days)^{*5} of the corresponding dose^{*2} between the scheduled study visits*/Period between the scheduled study visits (days)^{*4} \times 7

*: For each period between the scheduled study visits, the actual study visit dates will not be considered, and this variable should be fixed as follows:

- ✓ The first day of the treatment period to Week 2 of the treatment period: The first day of the treatment period (Day 1) to Day 14
- ✓ Week 2 of the treatment period to Week 4 of the treatment period: Day 15 to Day 28
- ✓ The same shall apply thereafter, and the final period between the scheduled study visits should be Week 20 to Week 24 of the treatment period: Day 141 to a blood sampling day for hematological tests at Week 24 of the treatment period.

However, for subjects who discontinued their treatment, the final period between the scheduled study visits should be up to the day before discontinuation.

*2: If there are multiple applicable doses, the sum of the calculated values for each dose should be used.

*3: The number of days without drug administration other than drug interruption should not be excluded from the "period of administration (days)".

*4: 14 days up to Week 12 of the treatment period and 28 days after Week 12 of the treatment period. However, for subjects who discontinued their treatment, the final period between the scheduled study visits (days) should be the actual number of days until the day before discontinuation.

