*5: "Period from the day of administration of darbepoetin alfa to the day of next administration of darbepoetin alfa". However, the first treatment period (days) during the scheduled study visit period should be "period from the start date during the scheduled study visit period to the day before the day of the first darbepoetin alfa administration date after the start date during the scheduled study visit period" and the last treatment period (days) should be "from the last day of darbepoetin alfa administration during the scheduled study visit period to the day before the day of the last treatment or the day before discontinuation during the scheduled study visit period".

The following formula should be used when no darbepoetin alfa is administered during the scheduled study visit period.

Mean weekly dose of darbepoetin alfa = Weekly dose of darbepoetin alfa immediately before the schedule study visit period

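### In section 4.9 of both SAPs the darbepoetin mean weekly dose has no exception for drug interruption, so a held subject can be tabulated at the previous dose

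*SAP*

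**What the plan says.** Section 4.9 is essentially the same in the Phase 1 SAP and the final-data SAP. Each window's mean is the prescribed dose times its period of administration, divided by the window length. For darbepoetin the result is multiplied by 7.

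- **MT-6548, footnote 3:** "The number of days without drug administration other than drug interruption should not be excluded" from the period of administration. Missed days therefore stay in, and interruption days come out.
- **Window length, footnote 4, both arms:** "14 days up to Week 12 of the treatment period and 28 days after Week 12 of the treatment period". It is shortened for early discontinuation but not for interruption.
- **Darbepoetin, footnote 5:** the period of administration is the "Period from the day of administration of darbepoetin alfa to the day of next administration of darbepoetin alfa", with extra wording for the first and last part of a window. Interruption is not mentioned.
- **Darbepoetin, window without an injection:** "The following formula should be used when no darbepoetin alfa is administered during the scheduled study visit period". The value is the "Weekly dose of darbepoetin alfa immediately before the schedule study visit period" (final-data SAP: "Weekly dose of darbepoetin alfa immediately before the scheduled study visit period").

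The protocol makes darbepoetin holds foreseeable. Section 8.3.2 tells the investigator, above stated Hb thresholds, to "discontinue darbepoetin alfa injection and resume at 1 step reduced dosage after Hb falls to" a set level. Section 12.3 adds a temporary stop for raised ALT or AST. Section 4.5 of both SAPs identifies a darbepoetin interruption by a CRF dose entry of 0 µg.

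**The concern.** The carry-forward serves a real purpose. Darbepoetin may be given every 4 weeks, while windows up to Week 12 last 14 days, so some windows properly contain no injection. The difficulty is that the rule does not separate those windows from ones in which the drug was deliberately withheld. On the plain wording, a withheld subject appears at the earlier dose.

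Study drug dosage is a listed endpoint. It is summarised by visit window with time-course plots, by first-day Hb tertile, by site and by subgroup. Many holds are triggered by high Hb, so any error would fall on particular subjects and windows and would hide the withholding that these summaries ought to show.

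The SAPs could also disagree with themselves. Section 8.6.1.5 has a 0 µg weekly-dose category for adverse events, section 4.8 subtracts interruption days from the compliance denominator, and section 4.10 builds cumulative darbepoetin dosage from actual injections. The same held subject could sit at 0 µg in an adverse event table and at full dose in the dose table.

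**Working it through.** The documents state no dose figure or interruption rate to reproduce, so the check applies the section 4.9 formulas to illustrative subjects.

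**Inputs.** The window lengths of 14 and 28 days come from footnote 4. The illustrative doses are assumed from within the permitted range: MT-6548 300 mg/day, and darbepoetin 60 µg every 2 weeks. The prescribed injection is spread over its dosing interval: 60/14 × 7 = 30 µg/week.

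**Formulas.**
- MT-6548: dose × (window − interruption days) / window.
- Darbepoetin as written: the prior weekly dose continues until the next injection, or is carried into a window with none.
- Darbepoetin with interruption days at zero: 30 × (window − interruption days) / window.

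| Window | Days held | MT-6548 | Darbepoetin as written | Darbepoetin, interruption = 0 |
|---|---|---|---|---|
| 28 days | 28 | 300 × 0/28 = 0 mg/day | 30 µg/week | 30 × 0/28 = 0 µg/week |
| 28 days | last 14 | 300 × 14/28 = 150 mg/day | 30 µg/week | 30 × 14/28 = 15 µg/week |
| 14 days | 14 | 300 × 0/14 = 0 mg/day | 30 µg/week | 30 × 0/14 = 0 µg/week |

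The same hold removes all or half of the MT-6548 dose and none of the darbepoetin dose.

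**Group mean for one window.** Suppose a share f of subjects is held for the whole window and all subjects had the same prior dose. The mean as written is 30. With interruption days at zero it is 30 × (1 − f). The overstatement is 1/(1 − f) − 1.

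| Assumed f | Mean, interruption = 0 (µg/week) | Overstatement |
|---|---|---|
| 2% | 29.4 | 2.0% |
| 5% | 28.5 | 5.3% |
| 10% | 27.0 | 11.1% |
| 20% | 24.0 | 25.0% |

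**Why the carry-forward itself must stay.** At 60 µg every 4 weeks the weekly dose is 60/4 = 15 µg. Without carry-forward, a 14-day window with no injection would wrongly show 0.

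**The case against.** The strongest reply is that the SAP already treats an interruption as a dose record of 0 µg. Section 4.5 dates the interruption from the administration date of that entry, section 8.6.1.7 describes 0 µg as a selected dose, and section 8.6.1.5 lists it as a dose category. Section 4.9 works from the prescribed dose and, in footnote 2, sums over several applicable doses. On that reading the 0 µg entry closes the previous period, the dose before a held window is 0, and the bias disappears. This stands to the extent that an overstated control-arm dose is a literal reading and not an established fact. It does not settle the matter. Section 4.9 never says so, the trigger is that no darbepoetin is administered, and a 0 µg record is not naturally an administration. Two programmers could produce different tables from the same data.

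A reader might also infer a large distortion. Take 60 µg every 2 weeks and a next injection 8 weeks later: 30 µg/week is carried against 60/8 = 7.5 µg/week, a 4-fold difference. That is one constructed subject, and the documents give no duration or frequency of holds. It is not a figure for any single window either: in 2-week windows the comparison is 30 against 30 in the first, then 30 against 0.

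Nor is it a fault in itself that the arms have different rules. One drug is a daily tablet and the other an injection every 1, 2 or 4 weeks. Their doses are in different units, and no between-arm dose test is planned.

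**Conclusion.** The point holds as a minor gap in a derived variable. Taken literally, section 4.9 shows a held darbepoetin subject at the previous weekly dose, while an MT-6548 hold counts as zero. Under that reading the error can only raise the darbepoetin mean. For a subject held throughout a window it is the whole prior dose (30 µg/week in the example). The group size is unknown: about 2% to 11% if 2% to 10% of subjects are held for a whole window, with equal prior doses. Those shares are assumptions.

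The effect is confined to the descriptive mean weekly dose and its summaries by visit window, site and subgroup. Cumulative dosage, compliance and the primary Hb analysis do not use this variable. The documents therefore do not support a claim that the control-arm dose is in fact overstated, or that any efficacy or safety conclusion would change.

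**What to change.** Add to footnote 5 and to the no-administration formula in section 4.9 of both SAPs: *A CRF entry of 0 µg (interruption as defined in section 4.5) ends the period of administration of the preceding dose, and days from that entry to resumption contribute 0 µg. In all other windows without an injection, including 4-weekly dosing and late or missed injections, the preceding weekly dose is carried forward as now.*

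Do not cap the carry-forward at the end of the prescribed dosing interval. That would zero ordinary late injections. A 60 µg 2-weekly dose followed by an injection on Day 17, which is inside the Week 2 visit range in protocol Table 9.1-1, would average 60/17 × 7 = 24.7 instead of 30 µg/week. Footnote 3 keeps missed MT-6548 days in, so a cap would create a new asymmetry in the other direction.

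The cost is this short addition to each SAP and a re-run of the dose tables. It uses the 0 µg entry already collected and changes no dosing rule. One side effect should be accepted knowingly. If 0 µg is entered partway through a dosing interval, the mean falls below the amount injected. With 60 µg every 4 weeks and 0 µg entered after 14 days, the 28-day mean is 15 × 14/28 = 7.5 µg/week, against 15 from the injection itself.

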4.10 Cumulative dosage

The cumulative dosage of the study drug is defined by the following formula.

Cumulative dosage of MT-6548 = 150 mg × Days of 150 mg administration + 300 mg × Days of 300 mg administration + 450 mg × Days of 450 mg administration + 600 mg × Days of 600 mg administration

Number of administration days of X mg* = Day when dose was changed from X mg – First day of X mg administration (not excluding the number of days of no drug administration)

If there are multiple applicable periods, the sum of them should be used.

*: X indicates each dose of MT-6548.

The cumulative dosage of darbepoetin alfa is the sum of individual doses of darbepoetin alfa × the number of administrations of individual doses.

4.11 Hb value increase rate

The Hb value increase rate is defined as the rate calculated using the following method.

✓ Hb value increase rate (g/dL/week):
(Hb value at Week 4 of the treatment period – Hb value at the start of the treatment period)/([Hb value measurement day at Week 4 of the treatment period – Hb value measurement day at the start of the treatment period]/7)

✓ Hb value increase rate (regression) (g/dL/week):
The slope of the regression line calculated based on the Hb values measured from the first day of the treatment period to Week 6 of the treatment period 6 and the measurement day (weeks from the first day of the treatment period) is defined as the Hb value increase rate (regression). Subjects without data at the first day and Week 6 of the treatment period should be excluded from the tabulation. The number of weeks from the first day of the treatment period used to obtain the regression line is defined by the following formula.

First day of the treatment period: 0

Week 2 of the treatment period: (Measurement day at Week 2 of the treatment period – the first day of the treatment period)/7

Week 4 of the treatment period: (Measurement day at Week 4 of the treatment period – the first day of the treatment period)/7

Week 6 of the treatment period: (Measurement day at Week 6 of the treatment period – the first day of the treatment period)/7

Unscheduled study visit from the first day of the treatment period to Week 6 of the treatment period: (Day of unscheduled study visit – the first day of the treatment period)/7

4.12 Iron supplement dosage

The dose of iron supplements is defined by the following formula. However, the dose of iron supplements will not be calculated if iron supplements are used as needed.

Mean monthly dose of iron supplements during the screening period* and each scheduled study visit period** (tabulation period of iron supplements) = (Daily dose based on the physician's prescription \times Period of administration (days) of the corresponding dose*** during the tabulation period of iron supplements)/Tabulation period of iron supplements (days)**** \times 30.4375****

*: The number of days of the screening period is “First day of the treatment period – First day of the screening period”.

**: For each period between the scheduled study visits, the actual study visit dates are not considered, and this tabulation is fixed as follows:

- ✓ The first day of the treatment period to Week 2 of the treatment period: The first day of the treatment period (1 day) to 14 days
- ✓ Week 2 of the treatment period to Week 4 of the treatment period: 15 to 28 days
- ✓ The same shall apply thereafter, and the final period between the scheduled study visits should be Week 20 to Week 24 of the treatment period: 141 days to a blood sampling day for hematological tests at Week 24 of the treatment period. However, for subjects who discontinued their treatment, the final period between the scheduled study visits should be up to the day before discontinuation.

***: If there are multiple applicable doses, the sum of the calculated values for each dose should be used.

****: For subjects who discontinued their treatment, the final period between the scheduled study visits (days) should be the actual number of days until the day before discontinuation.

*****: In this tabulation, 1 month month is counted as 30.4375 days (365.25/12 = 30.4375).

4.13 QOL (EQ-5D-5L) index value

Responses to five questions (mobility [Mo], self care [Sc], usual activities [Ua], pain/discomfort [Pd], anxiety/depression [Ad] in 5 levels (level 1 is healthy and the level goes up to 5, and the health status decreases with increases in level) are converted into index values. The index value is calculated using the Japanese EQ-5D-5L conversion table (Table 4.12.1) [1].

- (1) The responses to questions from Mo to Ad should be arranged side by side into five numbers (hereinafter, health state). The health state can exist from “11111” to “55555”.
- (2) If all five responses are 1, i.e. the health state is “11111”, the index value is 1. If the health state is other than “11111”, “Constant term: -0.060924” in Table 4.12.1 and the estimated value of the coefficient for each level

16.1.9 Documentation on Statistical Methodology

Confidential

of the response to each question should be used to obtain the index value using the following formula. The index value of the subject should be missing if one of the 5 questions has not been answered.

Index value = 1 + “Estimate of the constant term” + “Sum of ‘estimated coefficients corresponding to levels of responses other than 1’”

Table 4.12.1 Japanese EQ-5D-5L conversion table

Item	Level	Estimate	Standard error	p value
Constant term		-0.060924	0.013625	<0.0001
Mo	2	-0.063865	0.008996	<0.0001
	3	-0.112618	0.009287	<0.0001
	4	-0.179043	0.010231	<0.0001
	5	-0.242916	0.009425	<0.0001
Sc	2	-0.043632	0.008931	<0.0001
	3	-0.076660	0.009972	<0.0001
	4	-0.124265	0.010129	<0.0001
	5	-0.159659	0.008924	<0.0001
Ua	2	-0.050407	0.009205	<0.0001
	3	-0.091131	0.010005	<0.0001
	4	-0.147929	0.009744	<0.0001
	5	-0.174786	0.009115	<0.0001
Pd	2	-0.044545	0.008354	<0.0001
	3	-0.068178	0.010052	<0.0001
	4	-0.131436	0.008985	<0.0001
	5	-0.191203	0.009604	<0.0001
Ad	2	-0.071779	0.009701	<0.0001
	3	-0.110496	0.010863	<0.0001
	4	-0.168171	0.009850	<0.0001
	5	-0.195961	0.009164	<0.0001

Mo: mobility, Sc: self care, Ua: usual activities, Pd: pain/discomfort, Ad: anxiety/depression

4.14 QOL (KDQOL) scoring

Step 1 (See Table 4.13.1[2]): The appropriate score is converted from the response choices for each item number in Table 4.13.1 [2] (See Listing 16.2.4.9 for questions) for each subject.

Table 4.13.1 Step 1 in KDQOL scoring [2]

Item number	Response choices	Score
Question 4, A–D Question 5 A–C, Question 21	1	0
	2	100
Question 3 A–J	1	0
	2	50
	3	100
Question 19 A, B	1	0
	2	33.33
	3	66.66
	4	100
Question 10 Question 11 A, C Question 12, A–D	1	0
	2	25
	3	50
	4	75
	5	100
Question 9 B, C, F, G, I Question 18 B	1	0
	2	20
	3	40
	4	60
	5	80
	6	100
Question 20	1	100
	2	0
Question 1, Question 2, Question 6, Question 8 Question 11 B, D, Question 14 A–M, Question 15 A–H, Question 16 A, B Question 19 A, B	1	100
	2	75
	3	50
	4	25
	5	0
Question 7 Question 9 A, D, F, H Question 13 A–F Question 18 A, C	1	100
	2	80
	3	60
	4	40
	5	20
	6	0
Question 23	1	100
	2	83.33
	3	66.66
	4	50
	5	33.33
	6	16.66
	7	0

Step 2 (See Table 4.13.2[2]): The mean of the scores calculated at Step 1 in the item numbers in the right column of Table 4.13.2 [2] is calculated for each subject by subscale. For questions 17 and 22, the scores obtained are multiplied by 10 to convert the values from 0 to 100. The mean value should be the score for each subject by subscale. If at least one question constituting the subscale is answered, the subscale should be tabulated without missing. If 'No' is chosen in question 16, the question 16 should be treated as missing.

Table 4.13.2 Step 2 in KDQOL scoring [2]

Each item score should be averaged to calculate each subscale score

Subscale	Number of items	After scoring according to Table 4-1, the mean of the items included in each subscale should be calculated.
Kidney disease-specific scale		
Symptoms	12	Questions 14 A–K, L (M)*
Effects of kidney disease on daily life	8	Question 15 A–H
Burden due to kidney disease	4	Question 12 A–D
Working status	2	Question 20, Question 21
Cognitive function	3	Question 13 B, D, F
Relationship with people	3	Question 13 A, C, F
Sexual function	2	Question 16 A, B
Sleep	4	Question 17, Question 18 A–C
Social support	2	Question 19 A, B
Encouragement from dialysis staff	2	Question 24 A, B
Patient satisfaction with dialysis care	1	Question 23
Comprehensive scale (SF-36)		
Physical functioning	10	Question 3 A–J
Daily role functioning (physical)	4	Question 4 A–D
Bodily pain	2	Question 7, Question 8
General health	5	Question 1, Question 11 A–D
Vitality	4	Question 9 A, E, G, I
Social functioning	2	Question 6, Question 10
Daily role functioning (emotional)	3	Question 5 A–C
Mental health	5	Question 9 B, C, D, F, H

4.15 Adverse drug reactions

Adverse events for which a causal relationship to the study drug was evaluated as “reasonable possibility” are defined as adverse drug reactions.

5. Analysis Sets

Efficacy analysis will be performed in the largest analysis set (hereinafter, FAS). Primary endpoint analysis will also be performed with the set of subjects conforming to the protocol, or the per-protocol set (PPS). Safety analysis will be performed in the safety analysis set. Pharmacokinetic analysis will be performed in the pharmacokinetics analysis set.

The analysis sets are defined below; Details of treatment period phase 1 fixed data and treatment of subjects with final fixed data will be determined by the sponsor by the time the data are fixed.

5.1 Efficacy analysis set

(1) FAS

The FAS consists of all randomly allocated subjects excluding the following subjects:

- ✓ Subjects who did not have anemia associated with NDD-CKD
- ✓ Subjects who have never received a dose of the study drug
- ✓ Subjects with no post-randomization efficacy data

(2) PPS

PPS is defined as the analysis set consisting of subjects excluding the following subjects from the FAS.

- ✓ Subjects who deviated from inclusion criteria
- ✓ Subjects who met any of the exclusion criteria
- ✓ Subjects who violated rules concerning prohibited concomitant drugs or therapies
- ✓ Subjects with a <80% compliance rate for either MT-6548 tablets or darbepoetin alfa injection

